6. STUDY DESIGN

6.1.Design

Multi-site extension study of the APLICOV-PC clinical study follow-up.

The plitidepsin doses considered in this trial include the three doses specified in the APLICOV-PC study:

- 1.5 mg of plitidepsin administered as a 1.5-hour infusion, once a day for 3 consecutive days (total dose 4.5 mg).
- 2.0 mg of plitidepsin administered as a 1.5-hour infusion, once a day for 3 consecutive days (total dose 6.0 mg).
- 2.5 mg of plitidepsin administered as a 1.5-hour infusion, once a day for 3 consecutive days (total dose 7.5 mg).

6.2.Primary endpoint

Incidence of complications related to COVID-19 infection.

Evaluation of the principal variable:

The following information will be gathered in this study:

- Readmissions to hospitals and causes, from the last visit of the APLICOV-PC study to the end of the extension study.
- Need for oxygen therapy and duration of the same, from last visit of APLICOV-PC study until the end of the extension study.
- Presence of complications (see annex 5) since last visit of APLICOV-PC study until the end of this extension study by the patient.

Also, once the informed consent has been signed, the following tests will be carried out in the following 7 days:

- Barthel Index [26], to assess the patient's degree of autonomy when performing activities of daily living.
- Evaluation of the dyspnea, according to the mMRC scale [27].
- Evaluation of functional capacity (6 minute walk test) [28].
- Physical examination, including weight, height, BSA, pulse oximetry, PAI (estimated annex 8).

- Full analysis, including inflammation markers.
- Chest X-ray, in patients diagnosed with pneumonia upon admission to hospital, which led to their participation in the APLICOV-PC study.
- Evaluation of pulmonary function, including dyspnea evaluation (mMRC and 6 minute walk test) (annexes 7 and 9) SaO₂, PAFI (direct or estimated) (annex 8), spirometry (forced vital capacity, FEV1 and FEV1/CVF) and the diffusion test.
- Electrocardiogram.
- Heart Ultrasound/MUGA, in patients that suffered a relevant cardiac event while participating in the APLICOV-PC study or in those patients for which it was clinically indicated during follow-up.
- Thus, an evaluation was made of both the ultrasound images and the results of the complementary (analytical or functional) tests necessary for interpreting the long-term evolution of the disease, from the start of the patient's participation in APLICOV-PC to the end of this study.

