6.3. Secondary outcomes

Not applicable.

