12.4. Analysis of the primary endpoint

The main objective of the study is to evaluate the incidence of post-COVID morbidity and characterize the complications profile in the cohort of patients who participated in the APLICOV-PC study.

The number and percentage of patients who develop complications related to persistent illness, as judged by a physician, during the period between the end of the APLICOV-PC proof of concept study and the end of this extension study by the patient, as well as the percentage of patients who present complications.

A description of the following endpoints will also be presented:

- Number and percentage of patients who required readmission to hospital and causes, since last visit of APLICOV-PC study until the end of this extension study.
- Need for oxygen therapy and duration of the same, since last visit of APLICOV-PC study until the end of this extension study.
- The maximum, minimum, Q1 and Q3, mean, median and standard deviation of the duration of the oxygen therapy will be provided.
- Number and percentage of patients who presented complications (see annex 5).
- Barthel Index [\[26\]](#). A description will be provided with the frequency and percentage of each dependency category according to the score obtained:
 - 0-20: Total dependency
 - 21-60: Severe dependency
 - 61-90: Moderate dependency
 - 91-99: Slight dependency
 - 100: Independence
- The maximum, minimum, Q1 and Q3, mean, median and standard deviation of the parameters related to pulmonary function will be provided: SaO₂, PAFI, CVF, FEV1, FEV1/CVF and diffusion test.
- The maximum, minimum, Q1 and Q3, mean, median and standard deviation of the results of the 6 minute walk test will be provided.
- A description will be provided with the frequency and percentage of each category of the mMRC scale.
- Number and percentage of patients with abnormalities in the chest X-ray, in patients who present pneumonia upon entry into the APLICOV-PC study, and description of the abnormalities.
- Number and percentage of patients who presented abnormalities $\geq G2$ in the analytical parameters.
- Number and percentage of patients who presented abnormalities in the ECG, and description of the abnormalities.
- Number and percentage of patients who presented abnormalities in the heart Ultrasound/MUGA in patients who suffered a relevant cardiac event during their participation in the APLICOV-PC study, and description of the abnormalities.

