Annex 5. Post-COVID complications

	List of post-COVID complications		
COMPLICATIONS	HAVE HAD	Duration	Worst grade
Fatigue/asthenia	YES/NO	Start/end date	
General malaise	YES/NO	Start/end date	
Headaches	YES/NO	Start/end date	
Low mood	YES/NO	Start/end date	
Muscle aches and pains	YES/NO	Start/end date	
Joint pains	YES/NO	Start/end date	
Attention deficit	YES/NO	Start/end date	
Chest pressure	YES/NO	Start/end date	
Anxiety	YES/NO	Start/end date	
Febricula	YES/NO	Start/end date	
Cough	YES/NO	Start/end date	
Memory lapses	YES/NO	Start/end date	
Diarrhoea	YES/NO	Start/end date	
Palpitations	YES/NO	Start/end date	
Dizziness	YES/NO	Start/end date	
Tingling in extremity	YES/NO	Start/end date	
Others (specify)	YES/NO	Start/end date	

List based on the survey carried out by the Spanish Society of General Practitioners and Family Doctors.

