2.2 Justification of the study

The APLOCOV-PC proof of concept study demonstrated the antiviral activity of plitidepsin in terms of viral load reduction, recovery induction, lymphocyte and other inflammatory parameters reconstitution.

Approximately 10 to 25% of patients with COVID-19 experience symptoms beyond 3 months, resulting in a significant restriction in their everyday lives due to the sequelae of the disease that may persist for a year or more and entail long-term medical leaves.

The aim of this study is to assess whether the treatment with plitidepsin, by attaining a reduction in the viral load and a faster recovery of the patient, could have a relevant impact in preventing the appearance of sequelae resulting from the SARS-CoV-2 infection.

23 Code of the study

E-APLOCOV-PC (AV-APL-A-003-21).

24 Sponsor

Pharma Mar, S.A

25 Design

Multi-site extension study of the APLOCOV-PC clinical study follow-up.

To participate in the study, the patients must have previously participated in the APLOCOV-PC proof of concept study and may have received:

- 1.5 mg of plitidepsin administered as a 1.5-hour infusion, once a day for 3 consecutive days (total dose 4.5 mg).
- 2.0 mg of plitidepsin administered as a 1.5-hour infusion, once a day for 3 consecutive days (total dose 6.0 mg).
- 2.5 mg of plitidepsin administered as a 1.5-hour infusion, once a day for 3 consecutive days (total dose 7.5 mg).

Patients were enrolled after signing informed consent to participate in this extension study.

26 Study Objectives

To evaluate the incidence of post-COVID-19 morbidity and characterize the profile of complications in patients who participated in the APLOCOV-PC study.

27 Endpoints

Incidence of post-COVID-19 complications.

28 Study population

The main objective of the study is to evaluate the incidence of post-COVID-19 morbidity and

characterize the profile of complications in patients who participated in the APLICOV-PC study. The maximum number of patients who can participate in the trial is limited to 42.

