6.2 Patients characteristics

Demographic and baseline data:

- Age (years)
- Gender (male/female)
- Ethnic group (Arab; Caucasian; Latin; Asian; Black; Other)
- Weight (kg)
- Height (cm)
- Body surface area (BSA) (m²)
- Body mass index (BMI) - calculated

In addition to all the basal characteristics used in APLICOV-PC if it necessary.

7 Analysis of the primary endpoint

The main objective of the study is to evaluate the incidence of post-COVID-19 morbidity and characterize the profile of complications in the cohort of patients who participated in the APLICOV-PC study.

The number and percentage of patients who develop complications related to persistent illness, according to the physician, during the period between the end of the APLICOV-PC proof of concept study and the completion of this extension study by the patient, as well as the percentage of patients who present complications will be detailed.

A description of the following endpoints will be presented:

- Number and percentage of patients who required readmission to hospital and causes, since last visit of APLICOV-PC study until the end of this extension study.
- Number and percentage of patients who needed oxygen therapy and duration of the same, since last visit of APLICOV-PC study until the end of this extension study.
- The maximum, minimum, Q1 and Q3, mean, median and standard deviation (Std) of the duration of the oxygen therapy.
- Number and percentage of patients who presented complications (defined in Annex 5 of the protocol).
- Barthel Index. A description with the frequency and percentage of each dependency category, according to the score obtained, will be provided:
 - 0-20: Total dependency
 - 21-60: Severe dependency
 - 61-90: Moderate dependency
 - 91-99: Slight dependency
 - 100: Independence
- The maximum, minimum, Q1 and Q3, mean, median and Std of the parameters related to pulmonary function will be provided: oxygen saturation (SaO₂), ratio of partial pressure arterial oxygen and fraction of inspired oxygen (PAFI), forced vital capacity (FVC), forced expiratory volume in 1 second (FEV1), FEV1/FVC and diffusion test.

- The maximum, minimum, Q1 and Q3, mean, median and Std of the results of the Six-minute walk test (6MWT).
- Frequency and percentage of each category of the modified Medical Research Council (mMRC) scale:
 - 0 (Dyspnea only after strenuous exercise)
 - 1 (Dyspnea occurring when hurrying on level ground or walking up a slight incline)

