- Number and percentage of patients who have received any COVID-19 vaccine and the number of doses.
- Number and percentage of related or unknown post-COVID-19 complication. Worst per patient.
- Number and percentage of all post-COVID-19 complications. Worst grade per patient.
- Number and percentage of related post-COVID-19 complications. Worst grade per patient.
- Number and percentage of patients with at least AE.
- Number and percentage of patients with at least SAE.
- Number and percentage of patients with at least grade ≥ 3 AE.
- Number and percentage of patients with AEs by system organ classes (SOC) and preferred term (PT), regardless of relationship.
- The maximum, minimum, Q1 and Q3, mean, median and Std of laboratory parameters.
- Aplicov-pc summary of Demographic and Other Baseline Characteristics table of patients include in this study by dose and severity of disease.
 - Median (range) time from symptom onset to first plitidepsin administration, days
 - Number of comorbidities, n (%) (none, one, two or more)
 - Comorbidities, n (%) (Cardiac disease, Kidney disease, Liver disease, Lung disease (COPD), Asthma, Diabetes, Hypertension, Obesity)
 - Clinical status at randomization, n (%)
 - Vital signs, median (range) (Body temperature, $^{\circ}\text{C}$, Systolic blood pressure, mmHg,
 - Diastolic blood pressure, mmHg, Heart rate, bpm, Respiratory rate, bpm, SpO2
 - B, %, On oxygen at baseline, n (%))
 - Laboratory parameters, median (range) (WBC, $\times 10^9/\text{L}$, Platelet count, $\times 10^9/\text{L}$, Lymphocytes, $\times 10^9/\text{L}$, Serum creatinine, $\mu\text{mol}/\text{L}$, ALT \times ULN, AST \times ULN, LDH \times ULN, CPK \times ULN, GGT \times ULN, C-reactive protein, Ferritin, D-dimer)
 - log10 copies/mL viral load, median (range)
 - Days from Plitidepsin to first complication
 - Days from hospital discharge to first complication
 - Time from Plitidipesin first-dose to E-APLICOV inclusion (Month)

9 Listing

- Post-COVID-19 complications will be listed.
- Hospital readmission will be listed
- Oxygen therapy will be listed
- The medication administered before starting the 6MWT will be listed.
- The results of the ECG will be listed.

- The results of the chest X-ray will be listed.
- The ECHO/MUGA results will be listed
- The hematological laboratory parameters will be listed.
- The coagulation laboratory parameters will be listed.
- The biochemistry laboratory parameters will be listed.

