Appendix II

11 Primary endpoints

Table 11.1.1 End points I by dose cohort

Endpoints	Dose Cohort			
	1.5 mg N=X	2.0 mg N=X	2.5 mg N=X	Total N=X
	n (%)			
Patients who presented post-COVID-19 complications (related or unknown relationship to study disease)				
Patients who presented post-COVID-19 complications (regardless relationship)				
Patients who presented post-COVID-19 complications (related to study disease)				
Patients who required readmission to hospital (regardless of relationship)				
Patients who required readmission to hospital (COVID-19)				
Patients who required readmission to hospital (post COVID-19 complication)				
Patients who required oxygen therapy				
Patients with abnormalities in the chest X-ray*				
Patients who presented abnormalities $\geq G2$ in the analytical parameters				
Patients who presented abnormalities in the ECG				
Patients who presented abnormalities in the heart Ultrasound/MUGA**				

*Only in patients who present pneumonia upon entry into the APPLICOV-PC

** Only in patients who suffered a relevant cardiac event during their participation in the APPLICOV-PC study

Table 11.1.2 End points I by Severity of disease

Endpoints	Severity of disease			
	Mild N=X	Moderate N=X	Severe N=X	Total N=X
	n (%)			

Patients who presented post-COVID-19 complications (related or unknown relationship to study disease)				
Patients who presented post-COVID-19 complications (regardless relationship)				
Patients who presented post-COVID-19 complications (related to study disease)				
Patients who required readmission to hospital (regardless of relationship)				
Patients who required readmission to hospital (COVID-19)				
Patients who required readmission to hospital (post COVID-19 complication)				
Patients who required oxygen therapy				
Patients with abnormalities in the chest X-ray*				
Patients who presented abnormalities $\geq G2$ in the analytical parameters				
Patients who presented abnormalities in the ECG				
Patients who presented abnormalities in the heart Ultrasound/MUGA**				

*Only in patients who present pneumonia upon entry into the APLICOV-PC

** Only in patients who suffered a relevant cardiac event during their participation in the APLICOV-PC study

Table 11.2.1.1 Summary of post-COVID-19 complications, regardless of relationship, by dose cohort and overall. Worst per patient

Post-COVID-19 complications	Dose Cohort			
	1.5 mg N=X	2.0 mg N=X	2.5 mg N=X	Total N=X
	n (%)			
Asthenia				
General discomfort				

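### The study's only endpoint has no single case definition: the SAP tabulates three nested complication counts as primary endpoints, and neither document says which one is the incidence or is read against 15%

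*SAP*

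**What the plan says.** Protocol 6.3, "Secondary outcomes", is marked not applicable, so the complication incidence is the study's whole answer. It is worded in several ways:

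- **Protocol 6.2** (primary endpoint): "Incidence of complications related to COVID-19 infection". Relatedness is part of the definition.
- **Protocol 1.11 and the SAP synopsis** (Endpoints): "Incidence of post-COVID-19 complications" in the SAP's words, with no relatedness condition.
- **Protocol 12.4**: patients with "complications related to persistent illness, as judged by a physician", and, in the same sentence, the percentage with complications and no qualifier.
- **SAP 7**: the same pair of counts. The first is "The number and percentage of patients who develop complications related to persistent illness, according to the physician".
- **SAP Appendix II, Tables 11.1.1 and 11.1.2**, under a plural primary-endpoints heading: three rows. The first is "Patients who presented post-COVID-19 complications (related or unknown relationship to study disease", the second is regardless of relationship and the third is related to study disease. No row is marked as primary.
- **SAP 8**, as other analyses: the three categories again, including "Number and percentage of related or unknown post-COVID-19 complication. Worst per patient".

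Protocol 12.2 assumes a 15% incidence of post-COVID complications and rejects it in favour of 5% if 3 or fewer patients have them. It does not mention relatedness.

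Annex 5 ("List of post-COVID complications") records occurrence, dates and worst grade. SAP Listings 11.1.1 and 11.1.2 add a Relationship column. Neither document gives the categories of that variable, the criteria for assigning them, or how an unknown relationship is to be handled.

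**The concern.** The passages give different answers to the question of who is a case. Protocol 6.2 points to the related count. Protocol 12.4 and SAP 7 offer related and overall side by side. The SAP tables put first a category, related or unknown, that appears in neither protocol 6.2, protocol 12.4 nor SAP 7. They also use a different object of attribution: study disease in the tables, persistent illness in the text, COVID-19 infection in protocol 6.2.

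The distinction matters for this endpoint. Annex 5 lists fatigue, low mood, headache, anxiety and dizziness. Protocol 5.1 puts the available follow-up at almost 12 months, and new COVID-19 episodes and vaccination in the interval are recorded. A physician may reasonably be unable to attribute such a symptom to the original infection. Read literally, the related count treats every unknown as a non-case, in an unmasked single-arm study where every patient is known to have received plitidepsin.

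At stake is which percentage becomes the reported incidence, and which is compared with 15%. The multivariable analysis has the same gap: Table 11.13 reports odds ratios, which implies a binary outcome, but does not say which count is modelled.

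**Working it through.** **Inputs.** Maximum N = 42, null incidence 15%, alternative 5%, reject at 3 or fewer, one-sided alpha 0.05, power 80% (all protocol 12.2). The three counts are from SAP Table 11.1.1.

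**The plan's own figures.** The exact probability of meeting the rule is P(X ≤ 3) = Σ C(42, x) pˣ(1 − p)⁴²⁻ˣ for x = 0 to 3.

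- At p = 0.15: 0.1067 (stated alpha 0.05).
- At p = 0.05: 0.843 (stated power 0.80).

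The stated figures do not reproduce. That is a separate defect, and the present point does not depend on it. The rule is used below only as written.

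**The counts are nested.** Related ≤ related or unknown ≤ regardless. They may coincide. If they differ, they differ in that order.

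**One patient.** 1/42 = 2.4 percentage points, enough to move a count from 3 to 4.

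**Illustration.** Assumed split, not from the documents: 3 patients with a related complication, 2 more with unknown only, 2 more with unrelated only. The intervals are exact 95%, as protocol 12.1 provides for categorical variables.

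| Count | n/42 | Incidence | Exact 95% interval | 3 or fewer? |
|---|---|---|---|---|
| Related | 3 | 7.1% | 1.5% to 19.5% | Yes |
| Related or unknown | 3 + 2 = 5 | 11.9% | 4.0% to 25.6% | No |
| Regardless | 5 + 2 = 7 | 16.7% | 7.0% to 31.4% | No |

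The point estimates fall on both sides of 15% and only one count meets the rule. All three intervals contain 15%, so a reading based on the interval would not change.

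**How the rule behaves over a range of splits.** Assume an all-cause incidence of 15%, with each affected patient classed as related with probability r and unknown with probability u. Then p = 0.15 for regardless, 0.15(r + u) for related or unknown, and 0.15r for related.

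| r, u | P(≤ 3), regardless | P(≤ 3), related or unknown | P(≤ 3), related |
|---|---|---|---|
| 0.33, 0.33 | 10.7% | 39.2% | 84.7% |
| 0.50, 0.25 | 10.7% | 29.0% | 61.2% |
| 0.70, 0.15 | 10.7% | 20.0% | 34.4% |

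The values of r and u are assumptions; the documents give none. Over this range, moving from regardless to related multiplies the chance of meeting the rule by about 3 to 8 (34.4/10.7 = 3.2; 84.7/10.7 = 7.9), with no change in what happened to patients.

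**The case against.** Several objections have force.

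- **The protocol leans one way.** Protocol 6.2 and the first count in protocol 12.4 and SAP 7 point to physician-judged related complications. This stands as a leaning, but it does not settle the matter. The same sentence adds an overall count, and the SAP tables carry three rows without saying which one implements 6.2.
- **The analysis is mainly descriptive.** Protocol 12.1 says so, the SAP plans no test against 15%, and all three counts are tabulated by dose and by severity, with patient listings. This stands. A reader might infer that an unfavourable count could be hidden; the plan provides for showing every one.
- **The illustration is constructed.** This also stands. The 3/2/2 split is chosen to straddle the cut-off, and nothing in the documents says how often unknown will be recorded. The rows may differ; it cannot be said that they will.
- **Relationship is collected.** A reader might infer from Annex 5, which has no such column, that the judgement is never recorded. The documents do not support that. Listings 11.1.1 and 11.1.2 carry a Relationship column and Tables 11.2.2 and 11.3.2 depend on it. What is missing is a definition of the variable.
- **Timing.** The SAP was modified on 17 November 2022, after the planned end of inclusion in December 2021, and a reader might infer that the three-way split was introduced with results in view. The change history lists Table 11.1.2 as added but not Table 11.1.1, and neither document says whether any counts had been seen. That inference is not supported.

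None of these objections identifies which row is the study's answer.

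**Conclusion.** The point holds as a conflict between passages on the case definition of the only endpoint. No count is named as primary, and the benchmark and rule in protocol 12.2 attach to none of the three. The consequence is room for selective emphasis, or for selective use of the 15% benchmark.

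The size depends on how many patients fall between the rows. Each is worth 2.4 points at N = 42, and more if fewer enrol. Under the assumed 3/2/2 split the headline would range from 7.1% to 16.7%. If every complication were judged related, the three counts would be identical and the choice would not matter.

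The point should be resolved, because leaving it open weakens whichever incidence is reported and closing it costs almost nothing. It does not threaten the validity of the descriptive tables.

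**What to change.** 1. In SAP 7 and Table 11.1.1 (and 11.1.2), name one count as the primary incidence, and state that it is the count read against 15% and the outcome modelled in Table 11.13. Related or unknown is the conservative choice in an unmasked single-arm study, because an undecided attribution then counts against the treatment. It is already tabulated.
2. Mark related (the literal reading of protocol 6.2) and regardless as sensitivity results, always shown beside the primary count. Making related the primary count would stay closer to 6.2 and would also remove the ambiguity, but it treats unknowns as non-cases, and the SAP would have to say so.
3. Align the wording of protocol 6.2, 12.2 and 12.4 with the choice, using one term for the object of attribution.
4. Define the Relationship variable used in Listings 11.1.1 and 11.1.2: its categories, the criteria for each, who assigns it and when, and how unknown is handled.
5. Record in the SAP's change history whether any counts had been seen when the choice was made.

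The cost is a few sentences in the SAP, a short definition and a wording amendment to the protocol. Sample size and patient burden do not change. The downside is that the headline figure may be slightly higher than the related count.

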12. STATISTICAL CONSIDERATIONS

12.1. General considerations

This section describes the main analyses that will be carried out. The statistical analysis plan to be approved by the sponsor will include additional information on analyses, management of unavailable data and analytical methods. All data will be analysed with the SAS statistical analysis system, version 9.4. All analyses will be carried out mainly by descriptive statistical methods. Continuous endpoints will be described using maximum, minimum, Q1 and Q3, mean, median and standard deviation. Categorical endpoints will be described with frequencies and percentages as well as the exact 95% confidence interval of the relevant study variables. All results will be presented separately by treatment arm and severity of the information upon entry into the APLICOV-PC study.

The final statistical study that will be the basis of the study's final report, will cover the total population of patients once the extension study has ended.

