2.10 Exclusion criteria

There are no exclusion criteria for this study.

3 General principles

Planned analyses in this document will be carried out once the database is declared cleaned, closed and approved by Pharma Mar according to the premises described in the Data Management Plan version 1.0 approved on 12-Jan-2022.

Statistical analyses will be performed using Statistical Analysis System (SAS) software version 9.4 and RStudio. The results of the analyses will be presented in editable format (i.e. rtf).

The data will be provided with one decimal place in general. In those cases where greater precision is required, as many decimal places as necessary will be provided.

Before performing the analysis, the following terms should be coded/reviewed and approved:

- Adverse events (AEs), hospital readmissions and COVID-19 complications. Coded according to Medical Dictionary for Regulatory Activities (MedDRA) and graded according to the National Cancer Institute Common Terminology Criteria for Adverse Events (NCI-CTCAE) v5.
- Medication. Classified according to the WhoDrug dictionary (latest version available).
- Reconciliation between the clinical database and the Pharmacovigilance database of serious adverse events (SAEs) in the study, including the resolution of all discrepancies.

Analysis will be done separately for each arm and the total population.

Continuous variables will be presented through the mean, median, standard deviation, range, first quartile (Q1) and third quartile (Q3). Categorical variables will be displayed through the distribution of frequencies and percentages; percentages with valid data will be presented and missing values will not be taken into account in the percentage calculation.

4 Imputation

There is no strategies/methods to handle missing data.

5 Study analysis populations

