....				

Table 11.2.1.2 Summary of post-COVID-19 complications, regardless of relationship, by severity of disease and overall. Worst per patient

Post-COVID-19 complications	Severity of disease			
	Mild N=X	Moderate N=X	Severe N=X	Total N=X
	n (%)			

Anxiety				
Asthenia				
....				

Table 11.2.2 Summary of Complications, Related to study disease, by dose cohort and overall

Post-COVID-19 complications	Dose Cohort			
	1.5 mg N=X	2.0 mg N=X	2.5 mg N=X	Total N=X
	n (%)			
Asthenia				
General discomfort				
....				

Table 11.3.1 Summary of post-COVID-19 complications, by grade and overall. Worst grade per patient. (Dose 1.5 / 2 / 2.5 mg and total)

	Asthenia	G1		G2		G3			Total	
		N	%	N	%	N	%	N	%	N	%
Post-COVID-19 complications	Asthenia										
	...										
	...										
										

Table 11.3.2 Summary of post-COVID-19 complications, related to study disease, by grade and overall. Worst grade per patient. (Dose 1.5 / 2 / 2.5 mg and total)

	Asthenia	G1		G2		G3			Total	
		N	%	N	%	N	%	N	%	N	%
Post-COVID-19 complications	Asthenia										
	...										
	...										
										

Listing 11.1.1 Post-COVID-19 complications

Dose cohort	Subject id.	Post-COVID-19 complication	Start date	End date	Ongoing	Duration	First Date Plitidepsin dose	Relationship	Severity of disease

Listing 11.1.2 Post-COVID-19 complications (related to study disease)

Dose cohort	Subject id.	Post-COVID-19 complication	Start date	End date	Ongoing	Duration	First Date Plitidepsin dose	Relationship	Severity of disease

Table 11.4 Post-COVID-19 complications duration

Continuous endpoints	Dose Cohort																	
	1.5					...					Total							
	N	Mean	Median	Range	Q1	...	*	N	Mean	Median	Range	Q1
Post-COVID-19 complications duration																		
Asthenia																		
...																		

* Q3 and Std.

Listing 11.2 Hospital readmission

Dose cohort	Subject id.	Hospital readmission	Reason	ICU admission	Start date	End date	Ongoing	Duration

Table 11.5 Oxygen therapy duration

Continuous endpoints	Dose Cohort															
	1.5						...					Total				
	N	Mean	Median	Range	Q1	...*	N	Mean	Median	Range	Q1
Oxygen therapy duration																
Type**																

* Q3 and Std.

**Nasal cannula; Simple face mask; Venturi mask; Non-rebreather mask; Invasive mechanical ventilation (IMV); Other, specify

Listing 11.3 Oxygen therapy required

Dose	Subject id.	Oxygen therapy required	Type	Start date	End date	Ongoing	Duration

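### Duration Tables 11.4 and 11.5 have no rule or count for cases still ongoing at the single assessment, so if any case is ongoing the reported mean is biased, usually downward, by an amount the tables do not show

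*SAP*

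**What the plan says.** SAP Appendix II contains "Table 11.4 Post-COVID-19 complications duration", with one row per complication, and Table 11.5 for oxygen-therapy duration. Both give N, mean, median, range, Q1, Q3 and Std by dose cohort and in total. Neither has a column for ongoing or censored cases. SAP section 7 asks for "The maximum, minimum, Q1 and Q3, mean, median and standard deviation (Std) of the duration of the oxygen therapy", and protocol 12.4 asks for the same statistics. Complication duration is not named in SAP section 7 or protocol 12.4 and appears only as a table shell.

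Listing 11.1.1 (complications) and "Listing 11.3 Oxygen therapy required" have columns for start date, end date, ongoing and duration. Protocol Annex 5 records start and end dates.

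Protocol 12.1 hands the question to the SAP: "The statistical analysis plan to be approved by the sponsor will include additional information on analyses, management of unavailable data and analytical methods". SAP section 4 answers: "There is no strategies/methods to handle missing data". The only missing-value rule in SAP section 3 is that "missing values will not be taken into account in the percentage calculation", which does not concern durations.

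Under protocol section 10 all assessments fall between consent and day +7, with no later visit at which an open case could be closed.

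**The concern.** An ongoing case has a known start and no end. The plan can be run in two natural ways: set the duration to the time from start to visit (cut), or leave it blank so that the case falls out of the table (dropped). The SAP does not choose, both choices distort the mean, and a reader of the table alone could not tell which was used.

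Ongoing cases are plausible here. Protocol 5.2 says sequelae may continue for more than a year, and protocol 5.1 puts follow-up for the last parent-study patient at almost 12 months. The objective includes characterising the complications profile, and how long complications persist is part of that profile. If persistence is understated, the summary looks more favourable than the data warrant.

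**Working it through.** The plan gives no figure for duration or for the share of cases ongoing, so there is nothing to reproduce. The check has three parts: direction, illustrative size, and what happens with few patients.

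**Direction**

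- Cut: with true duration T and onset-to-visit time W, the recorded value is min(T, W), which never exceeds T. One ongoing case is enough to make the mean too low.
- Dropped: the long cases tend to be the ones lost, so the mean is usually too low. It is not always so. Take resolved cases of 6, 8 and 10 months plus a late-onset ongoing case that will last 1 month in all. The true mean is (6 + 8 + 10 + 1)/4 = 6.25; the mean without the ongoing case is 24/3 = 8.0.
- Median: it is safe only if cases are cut, all share about the same onset-to-visit window, and fewer than half are ongoing. With varying onset it fails. Take 6, 8, 10 and a 12-month case cut at 1 month. Only one in four is ongoing, yet the true median is (8 + 10)/2 = 9 and the cut median is (6 + 8)/2 = 7.

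**Illustrative size**

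Inputs:

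- Window. The last parent-study patient was included in November 2020 (protocol 5.1). Extension inclusion runs from October to December 2021 (protocol 1.14). The shortest window is therefore about 10 months (end of November 2020 to start of October 2021) to 14 months (start of November 2020 to end of December 2021).
- Persistence. Protocol 5.1 gives 10% symptomatic for at least 12 weeks and 0.8% beyond a year. These describe infected people generally, not this hospitalised cohort.
- Assumptions: exponential durations, onset at parent-study inclusion, and both percentages taken as shares of all infected.

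Mean duration: m = (52 − 12)/ln(10/0.8) = 40/2.526 = 15.84 weeks, or 3.65 months.

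With e = exp(−W/m): share ongoing = e; cut mean = m(1 − e); dropped mean = m − W·e/(1 − e).

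| W (months) | e | Cut mean | Low by | Dropped mean | Low by |
|---|---|---|---|---|---|
| 10 | 0.0646 | 3.41 | 6% | 2.96 | 19% |
| 12 | 0.0373 | 3.51 | 4% | 3.18 | 13% |
| 14 | 0.0216 | 3.57 | 2% | 3.34 | 8% |

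At W = 12 the true median is 3.65·ln 2 = 2.53 months. It is unchanged if cases are cut (the window is common here) and 2.40 if they are dropped.

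The result depends heavily on the assumptions:

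- If the 0.8% is a share of the 10%, then m = 40/ln(125) = 8.28 weeks = 1.91 months, and over the same windows the mean is 0.1% to 0.5% low if cut and 0.5% to 2.8% low if dropped.
- With onset 6 months before the visit and m = 3.65, e = 0.193, and the mean is 19% low if cut and 39% low if dropped.
- With an assumed mean of 6 or 12 months and W = 12, it is 14% or 37% low if cut and 31% or 58% low if dropped.

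**Few patients**

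The 15% incidence in protocol 12.2 applied to 42 patients gives 6.3, about 6 affected. With e = 0.0373, the chance that at least one of 6 is ongoing is 1 − (1 − 0.0373)^6 = 0.20, so under this illustration there is often no bias at all. When exactly one is ongoing at 12 months, its expected total duration is 12 + 3.65 = 15.65 months and the other five average 3.18. The expected true mean is (5 × 3.18 + 15.65)/6 = 5.26. The cut mean is (5 × 3.18 + 12)/6 = 4.65, 12% low. The dropped mean is 3.18, 39% low. The same data thus give about 4.7 or 3.2 months, depending on a choice that the SAP leaves open.

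**The case against.** The strongest reply has four parts.

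- **Little depends on duration.** The endpoint is incidence, the outputs are descriptive, and complication duration is not a named endpoint. This stands and sets the severity. It does not excuse Table 11.5, which serves an item in both documents' primary-endpoint sections.
- **The information is available elsewhere.** With at most 42 patients, ongoing cases can be counted from the listings. If they are dropped, N in Table 11.4 set against n in Table 11.2.1.1 hints at their number, though mixed with missing dates. This stands in part: if cases are cut there is no gap in N, and neither route shows how far the mean is off.
- **The Ongoing flag is a generic date field.** It also appears for readmission, COVID-19 history and medication. This is correct. The flag shows that the plan allows for ongoing cases, not that the sponsor expects them, least of all for oxygen therapy.
- **The percentages are assumptions.** This is also correct. The protocol's figure of about 30% of hospitalised pneumonia patients with fibrotic changes persisting for the first 12 months may suggest more persistence, but it concerns fibrotic lung changes, not the Annex 5 symptoms, and supplies no ongoing share.

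A reader might go further and infer that the tables will seriously understate persistence, or that the plan is tilted towards the treatment. The documents do not support either: they give no ongoing share, duration distribution or onset times, and there may be no ongoing case. The opposite inference, that the planned median is a safe fallback whenever fewer than half the cases are ongoing, fails once onset varies.

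**Conclusion.** The point holds and is minor. The duration tables apply complete-data statistics to data that may be right-censored, and no section of the protocol or SAP supplies the rule that protocol 12.1 left to the SAP. This goes beyond missing detail, because both natural ways of carrying out the plan misstate the mean as soon as one case is ongoing.

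The direction for cut cases is certain. For dropped cases it is usual, and certain only under conditions such as a common window. The size is unknown. The 2% to 6% and 8% to 19% ranges rest on exponential durations, onset at parent-study inclusion and general-population persistence, and should be read as illustration, not as a forecast for this cohort. For oxygen therapy the documents give nothing to compute from. Incidence, the per-patient listings and the readmission results are not touched.

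**What to change.** Add to the SAP: *Duration runs from start date to end date. If Ongoing = Yes, it is right-censored at the last date on which that item was collected.* For oxygen therapy that date must first be settled. Protocol section 10 footnote 16 stops collection at consent signing, while protocol 6.2, protocol 12.4 and section 10 footnote 4 run to the end of the extension study. These passages need to be reconciled.

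In Tables 11.4 and 11.5:

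- keep the planned statistics by dose cohort and total, labelled *observed duration to last assessment*;
- add the number ongoing to each cell;
- mark censored values in the range with '+'.

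For the overall complication row in the Total column only, add a Kaplan-Meier median with 95% CI ('NR' if not reached) and the proportion persisting at 3, 6 and 12 months. This needs one defined duration per patient, for example from first onset to resolution of the last complication. Leave single-symptom rows without it, as they are too sparse. State the CI type: with 6 cases of which only the longest is censored, the final Kaplan-Meier estimate is 1/6 with an upper limit of 0.517 on the log-log scale and 0.465 on the linear scale. The upper limit for the median is then not reached on the first scale and reached on the second.

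The cost is SAP wording, one count per cell and one standard procedure on data already collected. The statistics of protocol 12.4 stay, as does the protocol 12.1 rule "All results will be presented separately by treatment arm". The only protocol matter is the oxygen collection date. The downside is slightly more output and an imprecise Kaplan-Meier estimate with about 6 affected patients. The censoring rule and the ongoing count carry most of the benefit.
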